6.4 Exclusion Criteria

A patient must not be included in the study if any of the following criteria are true at the time of enrollment:

Gastrointestinal:

- Patient has undergone a gracilis neosphincter or insertion of an artificial bowel sphincter
- Patient has Inflammatory Bowel Disease (Crohn's disease, ulcerative colitis)
- Patient has a non-viable mucosal lining along the anal tract
- Patient has known significant pelvic floor prolapse, significant genitourinary prolapse beyond the introitus, significant symptomatic rectocele, or evidence of significant rectal evacuation disorder leading to post-defecatory leakage

- Patient has history of radiation treatment to the external anal sphincter or adjacent structures
- Patient does not agree to refrain from anoreceptive intercourse for the duration of the study

General:

- Patient is less than 18 years of age
- Patient is pregnant, breastfeeding, or plans to become pregnant during the course of the study
- Patient is morbidly obese (BMI ≥ 35)
- Patient has a neuromuscular disorder (e.g., muscular dystrophy, multiple sclerosis, fibromyalgia)
- Patient has uncontrolled type I or type II diabetes
- Patient has history of neoplasia within 5 years prior to enrollment, except for a cancer that was determined to be local occurrence only, such as basal cell carcinoma, or is receiving or planning to receive anti-cancer or anti-angiogenic drugs.
- Patient is not suitable for muscle biopsy as determined by physician
- Patient tests positive for Hepatitis B (required tests: Hepatitis B Surface Antigen [HBsAg] and Anti-Hepatitis B Core Total Antibody [Anti-HBc]), Hepatitis C (required test: Hepatitis C Antibody [Anti-HCV]), HIV (required tests: HIV Type 1 and 2 Antibodies [Anti-HIV-1, 2]).
- Tests positive for syphilis
- Human T-lymphotropic virus 1 (HTLV-1) antibody testing must be performed for donors living in, or originating from, high-incidence areas^a or with sexual partners originating from those areas or where the donor's parents originate from those areas (European sites only).
- Patient has known bleeding diathesis or uncorrected coagulopathy

^a Mainly found in selected geographically areas, the most significant of which are south western Japan, the Caribbean, Central Africa and some areas of South America.

- Patient has known allergy or hypersensitivity to bovine proteins or allergens, gentamicin sulfate, or ampicillin that medically warrants exclusion as determined by physician
- Patient has a compromised immune system due to disease state, chronic corticosteroid use or other immunosuppressive therapy
- Patient has any condition that would preclude treatment due to contraindications and/or warnings of concomitant medications or listed in the experimental product labeling
- Patient is simultaneously participating in another investigational drug or device study or the patient has completed the follow-up phase for the primary endpoint of any previous study less than 30 days prior to the first evaluation in this study
- Patient is unable or unwilling to provide informed consent
- Patient is unable or unwilling to commit to the follow-up procedures
- Patient has a medical condition or disorder that may limit life expectancy < two years or that may cause non-compliance with the protocol (e.g. unable to perform self-evaluations and/or accurately report medical history, incontinence symptoms, and/or data)

At Time of Cell Delivery:

- Patient is febrile (defined as temperature $\geq 38.5^{\circ}\text{C}$)
- Patient has current infection
- Patient has active anal fissure, anal fistula, rectal prolapse (full-thickness), or grade III or IV hemorrhoids

6.5 Point of Enrollment

Patients who meet the inclusion/exclusion criteria are eligible for entry into the study and will have the study protocol and potential risks and benefits of their participation in the study explained to them by the research coordinator and/or physician(s) as appropriate per institutional policy. Informed consent will be obtained in accordance with ICH GCP and applicable regulations, and each patient who agrees to participate in this study will be required to sign an informed consent document prior to any study procedure. Official enrollment will occur at the time of the biopsy.

6.6 Sample Size and Dose Allocation

The study will be undertaken at up to five investigative sites. A total of 50 patients will be treated with AMDC. There will be a minimum 1 week delay between the AMDC injection procedures for the first 5 patients.

All patients will receive a cell dose of 250×10^6 ($\pm 20\%$) cells. The Manufacturer will generate the appropriate cell dose and ship it to the Investigator for injection. All AMDC products will be transported in identical vials with the same volume of transport media and reconstituted to the same final volume prior to injection. Vials will be identified by a unique product lot number, which includes the patient identification number, patient initials, and date of collection.

6.7 Description of Methods at Patient Visits

The schedule of exams specific to study visits (time points) is provided in Table 6-1. A detailed study flow diagram is provided in Appendix A. Note that the time windows indicated for specific visits are suggested guidelines, not absolute requirements. The exams/tests specified at each visit (study time point) may be combined in any number of actual visits to accommodate site and patient scheduling as necessary.

Regarding study medications, there are no specific medication requirements for patients participating in this study. Patients are to be prescribed medications according to the standard of care at the respective investigative site. To the greatest degree possible, a patient's medication regimen related to fecal incontinence should be maintained constant during the entire course of the study. Patient medication usage will be captured in the medication log.

Table 6-1: Exam Visit Schedule

Study Time Point	Pre-enrollment Screening and Baseline ¹	Biopsy ¹	AMDC Injection Procedure	Post-treatment Follow-up ¹				
	Week -16 to -8			Day 0	Day 1 to 2	Month 1	Month 3	Month 6
	Visit 1	Visit 2	Visit 3		Phone	Phone	Visit 4	Visit 5
Informed Consent	X							
Patient History	X							
Medications Log	X	X	X	X	X	X	X	X
Blood-Borne Pathogens (HBV, HCV, Syphilis, HIV) ²		X						
Pregnancy Test ³	X	X	X					
Clinical Assessment ⁴	X		X			X	X	X
FIQL ⁵	X					X	X	X
Wexner Score	X					X	X	X
Patient Fecal Incontinence Diary ⁶		X	X			X	X	X
Endoanal Ultrasound	X ⁷							X
Anorectal Manometry	X ⁷							X
Muscle Biopsy		X						
AMDC Injection			X					
Phone Contact				X	X			
Adverse Events	X	X	X	X	X	X	X	X

¹ Exams/assessments may be completed at multiple actual visits as necessary to accommodate patient and hospital scheduling.

² If the biopsy procedure takes place more than 30 days after the blood-borne pathogens tests were completed during screening, the blood-borne pathogen tests (Hepatitis B, Hepatitis C, HIV, and syphilis) and risk assessment of HTLV-1 (and HTLV-1 antibody test if applicable) must be repeated before the biopsy procedure to confirm the patient's continued eligibility for study participation. Additionally, the blood-borne pathogens tests needs to be repeated at the time of donation or, if not possible, within seven days post donation.

³ Pregnancy test is not required if the patient has had a previous hysterectomy and/or is post-menopausal.

⁴ Clinical assessment (physical examination) includes visual inspection, digital rectal examination, and anoscopy and/or sigmoidoscopy at physician's discretion.

⁵ Fecal Incontinence Quality of Life Scale (FIQL).

⁶ The baseline Patient Fecal Incontinence Diary will be given out after the muscle biopsy and is to be completed prior to, and returned at, the injection procedure. A diary will be given at the injection and returned at the 3-month follow-up visit. During post-treatment follow-up, diaries are to be completed approximately 28-days prior to, and returned at, each designated visit.

⁷ Previous endoanal ultrasound and anorectal manometry exam results may be used for the baseline assessments as long as they: 1) were completed within 6 months prior to enrollment, 2) collected all required data, and 3) the patient did not undergo any procedures or change in condition since the exam that, in the physician's discretion, would be likely to invalidate the previous results.

6.7.1 Visit 1 (Week -16 to -8): Pre-enrollment Screening and Baseline

Informed consent will be obtained and patient medical history will be collected. A physical examination (clinical assessment), including a visual inspection, digital rectal examination, and anoscopy and/or sigmoidoscopy (at physician's discretion), will be performed. Blood samples will be collected to assess for blood-borne pathogens (Hepatitis B, Hepatitis C, syphilis, and HIV) and a risk assessment of HTLV-1 will be performed. If the biopsy procedure takes place more than 30 days after the blood-borne pathogen tests were completed during screening, the blood-borne pathogen tests (i.e. Hepatitis B, Hepatitis C, HIV, and syphilis) and risk assessment of HTLV-1 must be repeated before the biopsy procedure to confirm the patient's continued eligibility for study participation. If applicable, a urine sample will be collected from female patients for pregnancy testing (pregnancy test is not required if the patient has had a previous hysterectomy and/or is post-menopausal). During the visit, the patient will complete the FIQL and Wexner score questionnaires (administered by a member of the research staff). A log of the patient's current medications will be started. Patients will also be instructed not to change (to the greatest degree possible) their medication regimen, and other coping mechanisms, related to their fecal incontinence condition.

In addition, endoanal ultrasound and anorectal manometry tests will be performed prior to the biopsy. Previous exam results may be used for the baseline assessments as long as: 1) they were completed within 6 months prior to enrollment, 2) they collected all required data, and 3) the patient did not undergo any procedures or have any change in condition since the exam that, in the physician's opinion, would be likely to invalidate the previous results.

All pre-enrollment screening and baseline assessments (e.g. clinical assessment, urine test, ultrasound, manometry, and questionnaires) are recommended to be completed within eight weeks prior to enrollment. Blood tests must be performed within 30 days prior to the biopsy. These blood tests will be repeated prior to any additional biopsies, if more than one biopsy is required. Per manufacturing requirements, patients must be negative for the blood-borne pathogens of Hepatitis B (required tests: Hepatitis B Surface Antigen [HBsAg] and Anti-Hepatitis B Core Total Antibody [Anti-HBc]), Hepatitis C (required test: Hepatitis C Antibody [Anti-HCV]), HIV (required tests: HIV Type 1 and 2 Antibodies [Anti-HIV-1, 2]), syphilis and HTLV-1 (European sites only). At this point the patients will have completed all the necessary screening assessments and, if they meet all entry criteria, may now be enrolled into the study and can be scheduled for the muscle biopsy.

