2.2 Secondary Objectives

The secondary objectives are to study the effect of AMDC treatment for fecal incontinence on:

- Changes from baseline in the frequency and nature of incontinent episodes at 3, 6, and 12 months post-treatment as measured by a patient fecal incontinence diary

- Changes from baseline in Wexner incontinence score [1] (copy provided in Appendix B) at 3, 6, and 12 months post-treatment
- Changes from baseline in Fecal Incontinence Quality of Life Scale (FIQL) [2] (copy provided in Appendix C) scores at 3, 6, and 12 months post-treatment
- Changes from baseline in sphincter function as measured by anorectal manometry at 12 months
- Changes from baseline in sphincter morphology as measured by endoanal ultrasound at 12 months
- Safety as measured by adverse events

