6.7.2 Visit 2 (Week -8 to -6): Biopsy

After patient eligibility is confirmed, patients will return to the clinic for an outpatient procedure in which muscle tissue is obtained using a needle biopsy technique [REDACTED]. The blood-borne pathogens tests (Hepatitis B, Hepatitis C, syphilis, and HIV) and a risk assessment of HTLV-1 needs to be repeated at the time of donation or, if not possible, within seven days post donation. Note that several passes of the biopsy needle may be required to obtain a satisfactory sample of muscle tissue. Additionally, if the first biopsy does not produce

an adequate sample for product isolation, it may be necessary for the patient to return for another biopsy procedure. [REDACTED]

[REDACTED] If appropriate, patients will also have a urine sample collected for pregnancy testing, which would be repeated at any additional biopsy visits if more than one biopsy is required. The medication log will be updated if necessary and adverse events will be recorded and reported as appropriate. Additionally, patients will be given a 28-day diary to report fecal incontinence data and instructions on how to complete the diary. The diary should be started approximately 1 week after the biopsy procedure, completed during the subsequent 28 days, and returned to the site at the next scheduled visit (injection visit).

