6.7.3 Visit 3 (Day 0): AMDC Injection Procedure

[REDACTED] after the muscle biopsy, patients will return to the clinic for a brief outpatient procedure. Prior to injection, if appropriate, patients will also have a urine sample collected for pregnancy testing. Patients will also have their temperature measured and be assessed for signs of infection and changes in anorectal condition that may affect the "At Time of Cell Delivery" exclusion criteria. After confirming eligibility, the AMDC product will be prepared and injected into the external anal sphincter in accordance with instructions for use (as described in Section 3.3). Post-injection, injection sites will be inspected for the presence of bleeding or excessive trauma.

The medication log will be updated if necessary and adverse events will be recorded and reported as appropriate. Patients will be reminded not to change (to the greatest degree possible) their medication regimen, and other coping mechanisms, related to their fecal incontinence condition. Patients will be given a 28-day diary to report fecal incontinence data. The diary should be completed during the 28 days leading up to, and returned to the site at, the next scheduled visit (3 Month Follow-up Visit).

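### FIQL is scored only once before injection, nominally 8 to 16 weeks ahead and before the biopsy, so the reported post-treatment changes include any lasting change during the wait, which the schedule cannot measure

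*Combined protocol and SAP*

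**What the plan says.** The secondary objectives in Section 2.2 concern the effect of AMDC treatment, and one of them is "Changes from baseline in Fecal Incontinence Quality of Life Scale (FIQL"), assessed 3, 6 and 12 months after treatment.

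The baseline for that change comes from Section 6.7.1, headed "6.7.1 Visit 1 (Week -16 to -8): Pre-enrollment Screening and Baseline", which states: "During the visit, the patient will complete the FIQL and Wexner score questionnaires". The same section says that screening and baseline assessments, questionnaires included, "are recommended to be completed within eight weeks prior to enrollment". Section 6.5 adds: "Official enrollment will occur at the time of the biopsy". The FIQL baseline therefore precedes the biopsy, which Section 6.7.2 places at Week -8 to -6.

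Table 6-1 marks FIQL at Visit 1 and then only at the Month 3, 6 and 12 visits. The text for the biopsy visit (6.7.2) and the injection visit (6.7.3) does not mention it. The Wexner score has the same schedule. The diary does not: Table 6-1, footnote 6, says "The baseline Patient Fecal Incontinence Diary will be given out after the muscle biopsy", and it is returned at the injection visit.

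Section 6.7 describes the visit windows as suggestions, not requirements. Section 7.2 plans descriptive summaries with 95% confidence intervals. It does not say which value is the baseline and plans no summary of the waiting period.

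**The concern.** All 50 patients are treated and there is no concurrent control (Section 6.1), so change from baseline is all the FIQL evidence the study will have. Between the baseline score and Day 0 the patient has a muscle biopsy, keeps a 28-day diary, waits for the cells to be expanded and anticipates treatment. If quality of life shifts for any of these reasons, or through the natural course of the condition, and the shift lasts to follow-up, it will appear in a change labelled post-treatment.

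The waiting period is also the only stretch in which each patient is observed before cell injection. FIQL is measured at its start and not at its end, so the study cannot show whether there was any shift. Section 6.9 says the data should help in planning a larger trial, and Section 7.1 refers to potential efficacy. A change that mixes the two periods serves neither purpose well.

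**Working it through.** The documents give no figure for this interval, so there is none to reproduce.

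**Inputs**
- Weeks from the FIQL baseline to injection, B: 8 to 16 (heading of 6.7.1).
- Weeks from injection to follow-up, F: 13, 26 and 52, taking Months 3, 6 and 12 at their nominal times (6.7.6 to 6.7.8).

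**Share of the measured interval that lies before injection** = B / (B + F)

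| Follow-up | F | B = 8 | B = 16 |
|---|---|---|---|
| Month 3 | 13 | 8/21 = 38.1% | 16/29 = 55.2% |
| Month 6 | 26 | 8/34 = 23.5% | 16/42 = 38.1% |
| Month 12 | 52 | 8/60 = 13.3% | 16/68 = 23.5% |

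**How firm the Month 3 range is**
- The window of 1 week either side gives 8/(8+14) = 36.4% to 16/(16+12) = 57.1%.
- If the questionnaires are done just before a Week -6 biopsy, which the eight-week recommendation allows although the Visit 1 heading does not, the lower end is 6/(6+13) = 31.6%.
- A repeat biopsy (6.7.2) or visits outside the suggested windows can lengthen the wait.

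**From share of time to bias.** Let Y1, Y0 and Yk be the scores at Visit 1, Day 0 and Month k. The planned change splits exactly:

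Yk - Y1 = (Y0 - Y1) + (Yk - Y0)

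Let d be the mean of Y0 - Y1, and let f be the fraction of d still present at Month k. Apart from the treatment effect and anything else that happens after injection:
- the planned change from Visit 1 carries f × d;
- the change from Day 0 carries (f - 1) × d.

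If the drift lasts (f = 1), the planned change carries all of d and the Day 0 change carries none. If it fades completely (f = 0), the planned change carries none and the Day 0 change carries -d. The contamination thus depends on d and f, not on the share of time. The documents give neither, and the present schedule cannot estimate d.

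**What a Day 0 score would show.** With equal SDs at the two visits and correlation r between them, the 95% half-width for the mean Visit 1 to Day 0 change in 50 patients is 1.96 × sqrt(2(1 - r)/50) SD. The documents give no r. Assuming r from 0.5 to 0.8:
- r = 0.5: 1.96 × sqrt(1.0/50) = 0.28 SD
- r = 0.8: 1.96 × sqrt(0.4/50) = 0.18 SD

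That is precise enough to reveal a moderate drift or to make one unlikely.

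**The case against.** A baseline taken before any study procedure is defensible. The intervention as delivered is biopsy, cell expansion and injection, and Visit 1 captures the net change over that whole course. A score on the day of injection may be disturbed by anticipation or by recovery from the biopsy. If those effects fade by Month 3, the Visit 1 baseline is the cleaner of the two. This stands, and it is why Day 0 should not simply replace Visit 1.

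FIQL is a secondary endpoint in a study whose primary objective is adverse events. The analysis is descriptive, and Section 6.9 concedes that the study is too small to settle effectiveness. This also stands and limits the consequence. Patients are asked at Visit 1, and reminded at injection, to keep medication and coping habits constant. That may reduce drift but does not measure it.

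Three stronger readings are tempting, and the documents do not support them:
- A reader might take 38-55% as the part of the Month 3 change that is spurious. It is only a share of nominal time.
- A reader might infer that any drift before injection biases all three changes by its full amount. That holds only if the drift persists undiminished.
- A reader might see selection on the entry score. FIQL is not an entry criterion. The Wexner score is (at least 9 at baseline, Section 6.3), so regression to the mean is a further issue for that score.

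**Conclusion.** The concern holds as a gap in measurement. With one FIQL score before injection, taken before the biopsy, any waiting-period change that persists to follow-up is included in the reported changes and cannot be separated from change after injection. The wait is 38-55% of the nominal Month 3 interval, 24-38% at Month 6 and 13-24% at Month 12. These figures assume the headed visit times and months of nominal length.

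The size and direction of any bias are unknown, because the documents give no information on drift or its persistence. They do not show that the planned FIQL changes are biased, or that Visit 1 is the wrong baseline. Given the secondary, descriptive role of FIQL, this is an inexpensive improvement rather than a flaw that undermines the study.

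**What to change.** 1. In Table 6-1 and Section 6.7.3, add FIQL at Visit 3, completed before injection. Add the Wexner score as well, so that the two questionnaires keep the same schedule.
2. In Section 7.2, state that the Visit 1 score is the planned baseline.
3. In Section 7.2, plan to report side by side, each with a 95% confidence interval: the planned changes from Visit 1 to Months 3, 6 and 12; the Visit 1 to Day 0 change; and the changes from Day 0 to Months 3, 6 and 12.
4. State with the results that the lead-in includes the biopsy, differs in length from follow-up and is not a matched control. It cannot address expectation after injection. Where the two sets of changes disagree, the Visit 1 to Day 0 change shows by how much.

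The cost is a short additional assessment at a visit that already takes place, for up to 50 patients, and a small protocol amendment. It helps only for patients not yet injected when it takes effect. The apparent improvement after injection may be smaller than the change from Visit 1.

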6.7.2 Visit 2 (Week -8 to -6): Biopsy

After patient eligibility is confirmed, patients will return to the clinic for an outpatient procedure in which muscle tissue is obtained using a needle biopsy technique [REDACTED]. The blood-borne pathogens tests (Hepatitis B, Hepatitis C, syphilis, and HIV) and a risk assessment of HTLV-1 needs to be repeated at the time of donation or, if not possible, within seven days post donation. Note that several passes of the biopsy needle may be required to obtain a satisfactory sample of muscle tissue. Additionally, if the first biopsy does not produce

an adequate sample for product isolation, it may be necessary for the patient to return for another biopsy procedure. [REDACTED]

[REDACTED] If appropriate, patients will also have a urine sample collected for pregnancy testing, which would be repeated at any additional biopsy visits if more than one biopsy is required. The medication log will be updated if necessary and adverse events will be recorded and reported as appropriate. Additionally, patients will be given a 28-day diary to report fecal incontinence data and instructions on how to complete the diary. The diary should be started approximately 1 week after the biopsy procedure, completed during the subsequent 28 days, and returned to the site at the next scheduled visit (injection visit).

